13.3.1.2. Death Classification and Reporting

Sufficient information will be required in order to properly classify the subject's death. The Investigator shall classify each subject death per the following definitions:

- Cardiac Death: A death directly related to the electrical or mechanical dysfunction of the heart.
- Sudden Cardiac Death (SCD): Natural death due to cardiac causes, indicated by abrupt loss of consciousness within one hour of the onset of acute symptoms; preexisting heart disease may have been known to be present, but the time and mode of death are unexpected. If time of onset cannot be determined, SCD will alternatively be defined as any unexpected cardiac death occurring out of the hospital or in the emergency room as dead on arrival.
- Non-sudden Cardiac Death: All cardiac deaths that are not classified as sudden deaths, including all cardiac deaths of hospitalized subjects on inotropic support.
- Non-cardiac Death: A death not classified as a cardiac death.
- Unknown Classification: Unknown death classification is intended for use only when there is insufficient or inadequate information to classify the death.

The CEC will review deaths and provide a final adjudication of the primary cause of death and cardiac classification.

Regulatory reporting of subject deaths will be completed according to local regulatory requirements.

13.3.2. Product Complaints

For devices that are market-released, product complaint reporting is applicable. This includes when an AE is related to a market-released device during the study. The reporting of product complaints is not part of the clinical study and should be done in addition to the Adverse Event reporting requirements. Refer to local regulations for reporting requirements.

Product Complaint: Any written, electronic or oral communication that alleges deficiencies related to the identity, quality, durability, reliability, safety, effectiveness or performance of a medical device that has been placed on the market.

It is the responsibility of the investigator to report all product complaint(s) associated with a medical device distributed by Medtronic, regardless whether they are related to intended use, misuse or abuse of the product. Reporting must be done immediately and via the regular channels for market-released products.

Medtronic will notify the regulatory authorities (e.g. FDA) as applicable for the following incidents immediately upon learning of them:

- Any malfunction or deterioration in the characteristics and/or performance of a device, as well as any inadequacy in the labeling or instructions for use which led or might have led to the death or serious deterioration in the state of health of a patient, user, or other person.
- Any technical or medical reason resulting in withdrawal of a device from the market by the manufacturer.
- A serious deterioration in the state of health includes:
 - Life-threatening illness or injury
 - Permanent impairment of a body function or permanent damage to a body structure
 - A condition necessitating medical or surgical intervention to prevent permanent impairment of a body function or permanent damage to a body structure

The investigator and Medtronic must abide by the reporting requirements shown in Table 7.

14. Data Review Committees

At regular intervals, an independent Clinical Events Committee (CEC) will review and adjudicate all reported adverse events and deaths for subjects participating in the study.

The CEC will consist of a minimum of three (3) non-Medtronic employed physicians that are not participating Investigators for the study, including a CEC chairperson.

Medtronic personnel may facilitate and participate in a CEC meeting but will be non-voting members.

For adverse events and deaths reviewed by the CEC, Medtronic will provide the CEC with the Investigator's description and classification. The CEC is responsible for reviewing the Investigator's assessment and supportive documentation (when available), reviewing applicable definitions, and determining final classifications for all adjudication parameters. Additionally, the CEC will provide an adjudication of the death classification for all reported deaths including primary cause of death and cardiac classification.

If the CEC disagrees with the Investigator's classification of the event, the rationale will be provided to the Investigator. If the Investigator agrees with the CEC's adjudication, the eCRF documenting the event will be updated accordingly.

If the Investigator does not agree with the CEC's adjudication classification, both determinations will be provided within the final report; however, the CEC's adjudication will be used for data analysis. The disagreement will also be included in reporting to IRB and regulatory authorities, if required.

15. Statistical Design and Methods

Medtronic employees will perform all statistical analyses.

Additionally, a separate Statistical Analysis Plan (SAP) will be developed to further describe statistical methods, pre-specified data handling rules (including how missing data will be handled), and pre-specified analyses, including subgroup analyses, that will be included in study reports (e.g. PMA report, final study report). Any deviation from the pre-specified statistical analyses will be noted in the study report.

The SAP will include a comprehensive description of the statistical methods and analyses to be included in reports that include analysis of endpoints. Any change to the data analysis methods described in the CIP will require an amendment to the CIP only if it changes a principal feature of the CIP. Any other change to the data analysis methods described in the CIP, and the justification for making the change, will be described in the clinical study report.

Additional exploratory analyses of the data may be conducted as deemed appropriate.

All objectives will be analyzed once all treated subjects complete the 12 month follow-up visit, or have exited the study. A final report will be completed after all subjects complete the final follow-up visit, or have exited the study. No interim analyses are planned.

The primary analysis will be conducted using a modified intent-to-treat protocol; all subjects for whom either AAD or cryoballoon ablation therapy is initiated will be analyzed according to their randomization status. Subjects who withdraw consent between randomization and initiation of therapy will be excluded from the primary efficacy analysis.

15.1. Primary Efficacy Objective

Demonstrate the superiority of cryoballoon ablation as compared to AAD therapy in terms of the rate of freedom from AF/AT/AFL in a non-drug refractory paroxysmal AF population.

15.1.1. Hypothesis

The hypothesis test used in assessment of the primary efficacy objective is that the proportion of subjects with treatment success at 12 months is greater in subjects randomized to cryoballoon ablation compared to subjects randomized to AAD therapy.

The following hypothesis will be tested in a two-sided test with $\alpha = 0.05$:

$H_0: \pi_{\text{cryo}} = \pi_{\text{AAD}}$

$H_a: \pi_{\text{cryo}} \neq \pi_{\text{AAD}}$

Where π_{cryo} and π_{AAD} are the proportion of treatment successes at 12 months in the modified intention-to-treat cohorts of the cryoballoon ablation and AAD groups, respectively.

15.1.2. Endpoint Definition

A treatment success is the opposite of a treatment failure.

A subject is considered a treatment failure if he/she experiences any of the following:

- Acute procedural failure (defined in section 5.1.4.1; treatment arm only)
- Documented AF/AT/AFL on ambulatory monitoring/12-lead ECG after the 90 day post-ablation blanking period (treatment arm)/AAD optimization period (control arm).
 - Minimum of 30 seconds on ambulatory monitoring or 10 seconds on 12-lead ECG.
 - Note: Documented occurrence and treatment of typical right-sided cavotricuspid isthmus dependent atrial flutter is not considered a failure if confirmed by entrainment maneuvers during EP testing.
- Any subsequent AF surgery or ablation in the left atrium.
- Any subsequent cardioversion after the 90 day post-ablation blanking period (treatment arm)/AAD optimization period (control arm).
- Class I or III antiarrhythmic drug (or sotalol) use after the 90 day blanking period (treatment arm only).

The AAD optimization period is defined as the first 90 days after AAD initiation (control arm). The blanking period is defined as the first 90 days after the index ablation procedure (treatment arm). Recurrences of atrial arrhythmias during the AAD optimization/blanking periods will not be counted in the determination of the first clinical failure for the primary endpoint. Within the 90 day AAD optimization period and 90 day post-ablation blanking period, recurrent arrhythmias can be managed with medications or cardioversions.

15.1.3. Performance Requirements

If a two-sided log-rank test shows the difference in 12-month success rates to be less than the pre-specified alpha of 0.05, the null hypothesis (that cryoballoon ablation has similar 12-month efficacy rates compared to AAD therapy) will be rejected in favor of the alternative hypothesis (that 12-month success

rates for subjects treated with cryoballoon ablation is greater than for those treated with AAD's), demonstrating the superiority of the cryoballoon ablation procedure for this endpoint.

15.1.4. Rationale for performance criteria

The performance requirement for this objective involves showing superior treatment efficacy rates through 12 months in a randomized study against the current standard of care, in a population of paroxysmal AF patients. The randomized nature of the study will provide the highest level of evidence that, in the event a statistically significant result is attained, that the treatment is indeed responsible for the difference in 12-month success.

15.1.5. Analysis Methods

The probability of a subject achieving success at 12 months (365 days) will be estimated using Kaplan-Meier survival analysis. The standard error will be approximated using Greenwood's formula. A two-sided 95% log-log confidence interval for the probability will be constructed. A two-sided log rank test with $\alpha = 0.05$ will be used to assess whether the failure rate differs between treatment groups.

Day 0 is defined as either the day of the index cryoablation procedure or the day in which AAD drug therapy is initiated. For subjects with treatment failure, the survival date will be set to the date of the treatment failure. For subjects without treatment failure through 12 months, those subjects will be censored at the last study contact date recorded on a CRF, which may include the last study visit, the exit date, or death date. If a subject without a treatment failure is lost to follow-up, the censoring date will be set to the last recorded study visit date. If treatment failure occurs on the day of index treatment, survival time will be set to 0.5 days.

If an occurrence of documented AF/AT/AFL resulted from rhythm monitoring that was initiated at the 12-month visit, then the date of occurrence used in the Kaplan-Meier analysis will be the minimum of 365 days from the cryoballoon ablation procedure/date of AAD initiation or the actual date of occurrence. This allows counting of all AF/AT/ AFL events found at the 12-month follow-up, even if the follow-up occurred after 365 days post-ablation.

The survival curves from 0 to 12 months will be presented for both treatment arms.

15.1.6. Sample Size

Sample size assumptions are:

- Two-sided chi-squared test
- Alpha=0.05
- AAD 12-month success rate = 45%
- Cryoballoon ablation group 12-month success rate = 69.9%
- Power>90%
- Attrition from randomization to 1 year = 10%

The above assumptions require 87 subjects per arm with data, or 174 total subjects. Adding in 10% attrition brings the overall randomized sample size to 194 for this objective. Note that a log-rank test will be used for the primary efficacy analysis, but the more conservative chi-squared test was used for sample size estimation.

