before ablation may be attempted. Pharmacological therapy for AF (paroxysmal and persistent) has limited antiarrhythmic efficacy, with recurrence of AF reported at 44% to 67% within one year, based on a systematic review of 45 randomized controlled clinical trials (Lafuente-Lafuente, Mouly, et al. 2006). Treatment with AADs may also result in an increased risk for adverse events. Results of an AFFIRM sub study showed that adverse events resulting in discontinuation of the treatment were common for AADs, occurring in 11.1% to 28.1% of patients, depending on the AAD used (AFFIRM First Antiarrhythmic Drug Substudy Investi. 2003). The RAAFT-2 study found that AAD's had a success rate of 42% at one year in 61 previously treatment-naive paroxysmal AF patients; meanwhile, the 2014 AHA/ACC/HRS guideline for the management of patients with AF stated that "much like other antiarrhythmic drugs, with the exception of amiodarone, the rates of maintaining sinus rhythm at 1 year for sotalol are 30 -50%" (January et. al. 2014) (Morillo, et al. 2014).

Atrial fibrillation is known to cause electrical remodeling of the atria as well as structural changes that promote perpetuation and progression of symptoms (Wijesurendra and Casadei 2015) (Shulka and Curtis 2014) (Jalife and Kaur 2015). Untreated PAF can give rise to persistent or permanent forms of the disease (De Vos, et al. 2010), which may be more resistant to contemporary AF treatments (Oral, et al. 2002) (Romero, et al. 2015). As such, early and effective intervention is key for normalizing sinus rhythm (SR) and preventing further remodeling and disease progression (Nattel, et al. 2014) (Cosio, et al. 2008). AAD treatments have little to no effect on remodeling (Nattel, et al. 2014) and although may restore SR in the short-term, have high long-term relapse rates (45-90%) (Cosio, et al. 2008) making this treatment largely ineffective at preventing progression of AF. By contrast, early evidence seems to indicate that catheter ablation may reverse indicators of structural remodeling associated with AF (Walters, et al. 2016) (Wu, et al. 2016). Furthermore, catheter ablation, particularly using the Arctic Front Advance™ Cardiac CryoAblation Catheter, hereafter also referred to as the cryoballoon, has a much higher efficacy rate and may be even more effective when provided earlier after AF onset (Arena, et al. 2016) (Tanner, et al. 2011).

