6.2. Rationale

The study has primary objectives designed to evaluate the safety and effectiveness of the Arctic Front Advance™ Cardiac CryoAblation Catheter for treatment of recurrent symptomatic paroxysmal AF. In the US, there are no ablation catheters approved to treat patients with paroxysmal AF unless they have demonstrated intolerance or refractoriness to anti-arrhythmic drug therapy. The study will provide patients with more options for treatment and the possibility of improving their health and quality of life and a decrease in stroke risk. If successful, the STOP AF First study will demonstrate meaningful therapeutic benefit in this population. This evaluation will support an indication expansion for the treatment of recurrent symptomatic paroxysmal AF. The study will be considered successful if it meets the primary objectives, contingent upon FDA review and approval.

The study will compare cryoablation to AAD therapy, the current standard of care for subjects experiencing atrial fibrillation for the first time.

Cryoablation efficacy will be demonstrated by showing that subjects in the cryoablation arm will experience a higher rate of efficacy success than the AAD arm (treatment success described in Section 5.1.4.1). The STOP AF Pivotal trial showed an efficacy success rate of 69.9%. Several trials were completed comparing radiofrequency ablation to AADs in the same non-drug refractory patient population (Nielsen, et al. 2012) (Morillo, et al. 2014) (Wazni, et al. 2005). The RAAFT-2 study monitored for recurrent arrhythmia in a manner similar to the requirements of this protocol; they required regular and symptomatic transtelephonic monitor transmissions (Morillo, et al. 2014). In RAAFT-2, approximately 45% of subjects in the AAD arm experienced recurrent atrial fibrillation by one year. The superiority analysis in this study is designed to show that subjects in the cryoablation treatment arm will experience less AF recurrence than subjects in the AAD arm, assuming similar recurrence rates to those in the STOP AF Pivotal trial and RAAFT-2.

Cryoablation safety will be demonstrated by showing that the rate of a pre-specified list of known potential complications is consistent with previous trials and current literature (Packer, et al. 2013).

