## 6.8. Changes to Planned Analysis

Additional details on analysis methods have been added to this SAP, but only [REDACTED] minor changes to the statistical methods defined in the STOP AF First CIP version 4 are noted. First, the definition of the PV stenosis component of this study's primary safety endpoint has been altered according to FDA study design considerations. The criteria of 70% PV area reduction stated in this document reflects this update, whereas the CIP version 4 shows the original definition of 75% reduction. Second, the sample size calculation for the primary efficacy analysis incorrectly states that Fisher's exact test was used in the

3

<https://www.fda.gov/downloads/RegulatoryInformation/LawsEnforcedbyFDA/SignificantAmendmentstotheFDCA/UCM365544.pdf>

<https://www.fda.gov/downloads/RegulatoryInformation/LawsEnforcedbyFDA/SignificantAmendmentstotheFDCA/UCM365544.pdf>

calculation. In actuality, a Pearson's chi-squared test was used, as stated in section 7.1 of this SAP, which led to the stated analytic sample size of 174. The significance of this edit is negligible, since in both cases the planned endpoint analysis involves using Kaplan-Meier methods, and the sample size for the study is driven by the primary safety endpoint. [REDACTED]

[REDACTED] Analytical deviations from procedures this SAP may be addressed by the release of newer SAP versions (if feasible), or will be described in the final report and/or main manuscript, along with the rationale for the deviation.

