### **7.1. Sample Size Determination for Primary Efficacy Objective**

Sample size was estimated using Proc Power in SAS v9.4. The calculation was done to find the number of analyzed subjects necessary to provide a two-sided Pearson’s chi-square test with  $\alpha = 0.05$  and 90% power to detect a difference between two binomial proportions, one of which was 69.9%, and the other 45.9%, under a 1:1 randomization ratio. The two groups’ rates represent the cryoablation and AAD arm 12-month success rates, respectively. The assumed cryoablation arm success rate was what was observed in the STOP AF pivotal trial. The AAD arm success rate estimate, 28 of 61 successes at one year, was observed under similar circumstances in the RAAFT-2 trial (Morillo, et al.).

[figure not shown]
Computed N Total	Actual Power	N Total
	0.901	174

This shows an analytical sample size of 174 subjects is required. However, it was assumed that 10% attrition would occur between enrollment and the 12-month follow-up. Therefore, the necessary enrollment calculated to yield a 90.1% probability of detecting the presumed treatment success difference is 194 subjects.

The sample size estimate attained based on using a chi-square test is conservative compared to the actual number of subjects required using the Kaplan-Meier methods described in 6.2.2, since in the latter case, attrition is partial: data is included for all subjects up until they exit the study, so only subjects who exit prior to day 0 (index ablation or AAD initiation) will provide no information to the analysis.

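### The protocol's efficacy sample size of 87 per arm does not follow from its stated 45% control rate, which needs 81; it follows from the SAP's 45.9%, and the RAAFT-2 figures in CIP 4.1 and 6.2 need reconciling with it

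*Protocol*

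**What the plan says.** CIP 15.1.6 sizes the primary efficacy comparison. Its listed inputs include "Two-sided chi-squared test", two-sided alpha of 0.05, power above 90%, "AAD 12-month success rate = 45" per cent, "Cryoballoon ablation group 12-month success rate = 69.9" per cent, and 10% attrition. It then states "The above assumptions require 87 subjects per arm with data, or 174 total subjects", and 194 randomised once attrition is added.

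SAP 7.1 reaches the same 174 and 194, but from two proportions, "one of which was 69.9%, and the other 45.9" per cent. It gives the source of the control rate as 28 successes among 61 subjects in RAAFT-2, and prints an actual power of 0.901. On the choice of test, SAP 6.8 says of the efficacy calculation: "In actuality, a Pearson's chi-squared test was used, as stated in section 7.1 of this SAP". It describes the Fisher's exact test named in CIP version 4 as a misstatement.

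The RAAFT-2 drug arm is also described in two other places in the current protocol:

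- CIP 4.1 says that the drugs "had a success rate of 42% at one year in 61 previously treatment-naive paroxysmal AF patients".
- CIP 6.2 says that "approximately 45% of subjects in the AAD arm experienced recurrent atrial fibrillation by one year", and adds that the superiority analysis assumes recurrence rates similar to those in STOP AF Pivotal and RAAFT-2.

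SAP 6.8 and 7.2 say that the safety objective drives the total of 210.

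**The concern.** A sample-size statement should be reproducible from the assumptions listed beside it. Here the protocol presents 87 per arm as what its inputs require, and a reader who runs the named test on those inputs gets a smaller number. The 0.9-point gap between 45% and 45.9% looks like harmless shortening of 28/61, but it changes the required size by 6 per arm.

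The second matter is what the 45% denotes. CIP 15.1.6 uses it as the success rate on drugs. CIP 6.2 attaches about the same figure, from the trial that the SAP names as its source, to recurrence, and links it to the design of the superiority analysis. A reader of the protocol alone cannot tell which is meant. This is a pivotal study intended to support a PMA supplement, so the planning rate should be stated once and agree across both documents.

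**Working it through.** **Inputs.** Two-sided alpha 0.05 (z = 1.960); power 90% (z = 1.2816); cryoballoon success p₂ = 0.699 (CIP 15.1.6, SAP 7.1); drug success p₁ = 0.459 (SAP 7.1) or 0.45 (CIP 15.1.6); 1:1 allocation; attrition 10%.

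**Formula.** Pearson chi-squared, pooled variance under the null, no continuity correction, with p̄ the mean of p₁ and p₂:

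n per arm = [1.960·√(2p̄(1−p̄)) + 1.2816·√(p₁(1−p₁) + p₂(1−p₂))]² / (p₂−p₁)²

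**Step 1: reproduce the SAP.** With p₁ = 0.459, p̄ = 0.579:

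- √(2·0.579·0.421) = 0.6982
- √(0.2483 + 0.2104) = 0.6773
- numerator (1.3685 + 0.8680)² = 5.002; denominator 0.240² = 0.0576
- n = 86.8, so 87 per arm and 174 in total
- 174/0.9 = 193.3, so 194 randomised
- power at 87 per arm = 90.05%, agreeing with the printed 0.901

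The SAP calculation and the attrition step are both correct.

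**Step 2: use the CIP's inputs.** With p₁ = 0.45, p̄ = 0.5745:

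- √(2·0.5745·0.4255) = 0.6992
- √(0.2475 + 0.2104) = 0.6767
- numerator (1.3704 + 0.8672)² = 5.007; denominator 0.249² = 0.0620
- n = 80.8, so 81 per arm and 162 in total
- 162/0.9 = 180 randomised
- power is 90.1% at 81 per arm and 92.0% at 87

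**Step 3: try other tests at 45% against 69.9%.**

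| Method | n per arm for 90% power |
|---|---|
| Pearson, pooled | 81 |
| Unpooled variance | 78 |
| Arcsine | 81 |
| Pearson, exact enumeration | 82 |
| Continuity-corrected, formula | 89 |
| Continuity-corrected, exact enumeration | 87 |
| Fisher's exact | 87 (89.6% at 86; 90.15% at 87) |

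So 87 can be reached at 45%, but only with a continuity correction, which neither document mentions, or with Fisher's exact test, which SAP 6.8 says was not used.

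**Step 4: efficacy power at the planned size.** The 210 randomised give 105 per arm; 105 × 0.9 = 94.5, and CIP 15.2.6 plans on 94 analysable in the cryoballoon arm. The same number is taken here for the drug arm.

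| Drug success | Power at 87 per arm | at 94 | at 105 |
|---|---|---|---|
| 45% (CIP) | 92.0% | 93.9% | 96.0% |
| 45.9% (SAP) | 90.1% | 92.1% | 94.6% |

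**Step 5: set the RAAFT-2 statements side by side.**

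| Place | Figure | Stated as |
|---|---|---|
| CIP 4.1 | 42%, 61 patients | success at one year |
| CIP 6.2 | about 45% | AF recurrence by one year |
| CIP 15.1.6 | 45% (source not named there) | 12-month success, used for sizing |
| SAP 7.1 | 28/61 = 45.9% | success at one year, used for sizing |

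Forty-two per cent of 61 is 25.6 patients, not 28, so the CIP 4.1 and SAP figures are not the same proportion. About 45% recurrence and about 45% success cannot describe one endpoint unless a tenth of the patients were neither. The documents do not say whether the endpoints or estimation methods differ.

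**The case against.** The case for leaving this alone is strong on consequence. SAP 7.1 sets out the calculation in full and it reproduces. At 45%, 87 per arm satisfies the CIP's own target of more than 90% power, so the only false part is the claim that the inputs require that number. The total of 210 comes from safety, and efficacy power exceeds 92% at 94 per arm under either sizing rate. All of that stands, and it limits the point to a correction of text. It does not make the statement in CIP 15.1.6 right, since a protocol reader does not see 45.9% there.

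It can also be said that 87 need not have come from 45.9%, because Fisher's exact test gives 87 at 45%. That is arithmetically true. It does not rescue the current text, which names chi-squared, while the SAP names Pearson and rules out Fisher. It does mean that one should not claim 45.9% as the only possible arithmetic route to 87; it is the documented one.

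A reader might infer something more serious from CIP 6.2: that 45% recurrence means 55% success on drugs. Under that rate 90% power would need 220 per arm, and power would be 52.8% at 87, 56.0% at 94 and 60.7% at 105. The documents do not support that reading. No section states 55%. It is a complement taken from a sentence about AF recurrence, whereas the trial's endpoint also fails on AT/AFL, later cardioversion, and left atrial ablation or surgery. The three stated success rates lie between 42% and 45.9%. An interchange of success and recurrence, or a different endpoint, would explain the sentence.

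**Conclusion.** The sample-size statement in CIP 15.1.6 is wrong as written: with the Pearson test, its inputs need 81 per arm (162 in total, 180 randomised), not 87 (174, 194). The stated 87 belongs to the SAP's 45.9%. The gap is 6 per arm, or 14 randomised subjects, and it errs on the safe side. The number randomised does not change.

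A reader might count four competing planning rates for the control arm. Only two, 45% and 45.9%, enter a sample-size calculation, and the first looks like a shortened form of the second. The 42% is a background citation and 55% is only an inference. What does stand is that CIP 4.1 and 6.2 do not agree with the planning rate, and that 6.2 ties its recurrence figure to the design of the superiority test. Which description of RAAFT-2 is correct cannot be settled from these documents.

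The arithmetic rests on the uncorrected Pearson test with 1:1 allocation, as SAP 6.8 and 7.1 describe. The planned analysis is a log-rank test, so the power figures are those of the sizing method, not of the final analysis.

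**What to change.** 1. In CIP 15.1.6, replace 45% with 45.9% (28/61, RAAFT-2) and name the test as Pearson's chi-squared. Then 87 per arm, 174, 194 and 90.1% power all reproduce and agree with SAP 7.1.
2. State the efficacy power at the size the trial will actually have: for 45.9%, about 92.1% at 94 analysable per arm and 94.6% at 105 per arm.
3. Check the RAAFT-2 figures in CIP 4.1 and 6.2 against the source and reconcile them with the planning rate. For each, say whether it is success or recurrence, for which endpoint, and, if the 42% and the 28/61 are both right, why they differ. The wording of 6.2 should follow from that check rather than be assumed here.

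The cost is a text correction in the protocol and one look at the cited publication. The number randomised, the analysis and the conduct of the trial are unaffected.
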